8.6.1 Additional Research Collection

This protocol will include residual sample storage for additional research. All samples, including all residual samples may be stored and the exploratory research with these samples described in the protocol may continue for 15 years post end of study, which is defined as 2 years after the final study report. The scope of work involves using serum, plasma, to assess markers of heart failure, cardiac remodeling, neurohormonal activation, angiogenesis, oxidative and myocyte stress, renal function, congestion, inflammation, and fibrosis and associated diseases and pathways. Work may also include studies on the HNO pathway and mechanism of action as well as any pathways impacted by BMS-986231, as well as development of new or improved assays for pathway and functional markers associated with either BMS-986231 and cardiovascular diseases. The goal is to better understand HF, cardiovascular and associated diseases/syndromes and any effects of the drug, BMS-986231.

Sites in the United States

Consent to additional research is required for all study participants, except where prohibited by IRB/ECs or academic/institutional requirements. Where one or more of these exceptions occurs, participation in the additional research should be encouraged but will not be a condition of overall study participation.

- If the IRB/ECs and site agree to the mandatory additional research retention and/or collection, then the study participant must agree to the mandatory additional research as a requirement for inclusion in the study
- If optional participation is permitted and approved, then the study participants may opt in or opt out of the additional research retention and/or collection

For non-US Sites

Additional research is optional for all study participants, except where retention and/or collection of such samples is prohibited by local laws or regulations, ECs, or institutional requirements. Participants (or legally authorized representatives, as applicable) will be required to provide separate informed consent to participate.

Sample Collection and Storage

All serum, plasma, and urine samples from PK, pharmacodynamic and exploratory biomarker collections (as defined in [Table 8](#), [REDACTED] may be retained for additional research purposes as described above. Samples kept for future research will be stored at the Sponsor biorepository or an independent, Sponsor-approved storage vendor.

- The manager of these samples will ensure they are properly used throughout their usable life and will destroy the samples at the end of the scheduled storage period, no longer than 15 years after the end of the study or the maximum allowed by applicable law
- Transfers of samples by research Sponsor to third parties will be participant to the recipient's agreement to establish similar storage procedures

All requests for access to samples or data for additional research will be vetted by the Sponsor to ensure the research supports appropriate research activities.

Samples will be stored in a coded fashion, and no researcher will have access to the key. The key is securely held by the investigator at the clinical site, so there is no direct ability for a researcher to connect a sample to a specific individual.

8.6.2 *Immunogenicity Assessments*

Not applicable.

8.7 *Health Economics OR Medical Resource Utilization and Health Economics*

Health Economics/Medical Resource Utilization and Health Economics parameters will not be evaluated in this study.

9 *STATISTICAL CONSIDERATIONS*

9.1 *Sample Size Determination*

The number of subjects to be enrolled was chosen based on practical considerations. Approximately 20 patients with HFrEF will be randomized in a 1:1 ratio to one of 2 sequences: BMS-986231/furosemide followed by placebo/furosemide or placebo/furosemide followed by BMS-986231/furosemide. The difference between BMS-986231 and placebo in total urine output in the 4 hours following furosemide administration will be estimated and presented with 95% confidence intervals (CIs).

Normal healthy volunteers have a urinary output around 0.5-1.0 mL/kg/H (40-100 mL/H), which could be decreased in people over 65 years old or patients with HF at around 0.2-0.5 mL/kg/H

(20-40 mL/H). Patients with HF given a bolus of IV loop diuretics is estimated to have their diuresis increased to 250-300 mL/H in the 4 hours following the administration. Assuming the standard deviation of urine output change is 20~35 mL/H based on the estimated range of the changes, with 20 patients, the study will be able to demonstrate a 20% increase in urinary output compared to placebo, with 90% power.

9.2 Populations for Analyses

For purposes of analysis, the following populations are defined:

Population	Description
Enrolled	All participants who sign informed consent.
Randomized	All randomized subjects who have started study drug infusion in at least one treatment period. This is also known as the Intent to Treat (ITT) population. Data in this data set will be analyzed based on randomized sequence of treatments.
Treated (per protocol)	All randomized participants who were given both study treatments and completed the study as per protocol. Participants will be included in the treatment group they received in each period.
Safety	All randomized participants who take at least 1 dose of double-blind study treatment. Participants will be included in the treatment group they received in each period.

9.3 Endpoints

9.3.1 Primary Endpoint

- The total volume of urinary output 4 hours after 40 mg furosemide bolus given to patients with HFrEF while on BMS-986231 compared to placebo: absolute difference in total volume and % change from placebo.

9.3.2 Secondary Endpoints

- FeNa, FeK, furosemide urinary and plasma concentration and ratio urinary sodium to urinary furosemide at 8 hours post-start infusion. Parameter values while patient is on BMS-986231 compared to placebo: absolute differences and % change from placebo.

9.3.3 Safety Endpoints

- Clinically relevant hypotension (defined as SBP < 90 mmHg or symptomatic hypotension) during infusion, incidence of AEs, abnormal clinical laboratory values, vital signs, ECGs, telemetry, physical examinations.

9.4 Statistical Analyses

The statistical analysis plan (SAP) will be developed and finalized before database lock and will describe the selection of participants to be included in the analyses, and procedures for accounting for missing, unused, and spurious data. Below is a summary of planned statistical analyses of the primary and secondary endpoints. For analyses involving baseline, the baseline value is defined as the last value prior to the start of infusion for the specific period, unless otherwise noted.

9.4.1 *Efficacy Analyses*

9.4.1.1 Primary Efficacy Analysis

All primary efficacy analyses will be performed using the treated (per protocol) population. Total amount of urine excreted over 4 hours after a bolus injection of 40 mg furosemide while receiving BMS-986231 or placebo will be summarized and analyzed. Volumes at each urinary collection

interval as well as total volume will be tabulated. Graphical presentations may be provided. All data will be listed.

A within patient analysis using a paired T-test will be performed to compare the volumes of urinary excretion and to test if there is a significantly different amount of urine secreted while receiving BMS-986231 versus placebo.

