The Bioanalytical Sciences section or its designate may be unblinded to the randomized treatment assignments, in order to minimize unnecessary assays of samples from subjects during the placebo treatment period. Likewise, the Metabolism and Pharmacokinetics section or its designate may be unblinded, if metabolite profiling work is conducted.

In certain circumstances, a pharmacokineticist or designate(s) in Clinical Pharmacology and Pharmacometrics, biostatistician(s) and programmer(s) at BMS, or designee, may be unblinded in order to prepare preliminary summaries of PK and safety data, as needed. These summaries will not reveal individual subjects' treatment sequence assignments.

6.4 *Dosage Modification*

BMS-986231 or placebo

The administration of the study drugs will be done through an infusion pump connected to a single peripheral IV line. After priming the infusion set tubing and connecting the lines to the IV catheter, the pump should be set to deliver the rates of infusion indicated on the infusion bag label.

The pump infusion volume display should be re-set to 0 after priming the infusion line and just prior to the start of the infusion, and the total volume infused at the conclusion of the infusion after 8 hours, or at the time of any early discontinuation, should be recorded in the clinic source documents.

[figure not shown]
At any time during the administration of study drug, the study drug infusion must be discontinued if an AE or any other safety issue suggests it is not in the patient's best interest to continue to receive study drug.

The investigator has the option to adjust the study drug dosage level downward by 50%, interrupt or discontinue the study drug infusion in patients that develop hypotension, or if the patient experiences symptomatic hypotension that is not easily tolerated, as follows (and shown in [Figure 2](#)):

- **Study drug reduction:** Study drug is decreased by 50% if SBP decreases to levels <90 mmHg but \geq 80 mmHg. The dose cannot be subsequently increased.
- **Study drug interruption:** Study drug is interrupted for 1 hour if SBP <80 mmHg or symptoms of low blood pressure occur. If the SBP is \geq 105 mmHg after one hour interruption, the study drug could be resumed at 50 % of the dose.
- **Study drug discontinuation:** Study drug will be permanently discontinued if SBP remains < 105 mmHg after 1 hour interruption or if SBP decreases to levels <80 mmHg or symptoms of low blood pressure occur.

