After a dose reduction, the dose cannot be increased again. Study drug will be permanently discontinued after it has been down titrated once, and criteria for dose reduction or interruption has been met again.

If an infusion in a given period is discontinued, patients remain eligible to complete the subsequent period.

Any decision to lower the dosage level of study drug or discontinue study drug should be based on the investigator's assessment of the patient's overall clinical stability, in the context of appropriate ongoing monitoring of the patient's condition.

A 50% dosage adjustment downward will be achieved by decreasing the rate of study drug infusion from 20 mL/H to 10 mL/H.

Furosemide will be administered through an IV bolus injection at H4 of study drug infusion. In the event the study drug has been reduced, furosemide injection is administered at H4 as planned. If the study drug has been temporarily interrupted, then restarted, furosemide will be administered after at least 4 hours of effective study drug infusion.

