- 3) No other immediately apparent possible causes of aminotransferase elevation and hyperbilirubinemia, including, but not limited to, viral hepatitis, pre-existing chronic or acute liver disease, or the administration of other drug(s) known to be hepatotoxic.

8.2.8 *Other Safety Considerations*

Any significant worsening noted during interim or final physical examinations, electrocardiogram, any other potential safety assessment required or not required by protocol should also be recorded as a nonserious or serious AE, as appropriate, and reported accordingly.

8.3 *Overdose*

All occurrences of overdose must be reported as SAEs (see Section [8.2](#)).

An overdose is defined as the accidental or intentional administration of any dose of a product that is considered both excessive and medically important. All occurrences of overdose must be reported as an SAE (see Section 8.2).

BMS-986231

Since there is limited clinical experience with BMS-986231, there is no current knowledge with overdosing, hence no specific guidance is currently available. In case of acute overdose, it is not known if dialysis would accelerate drug clearance. BMS-986231 produces vasodilation as a component of its hemodynamic effects. Thus, the most immediate adverse effect in the case of overdose of BMS-986231 may be hypotension, mediated at least in part by mechanisms similar to the hypotensive activity of IV nitroglycerin through activation of soluble guanylate. No specific pharmacologic antidote to HNO effects exists. In previous studies with BMS-986231 in healthy volunteers and advanced HF subjects, cessation of drug was adequate to restore blood pressure within 1-2 hours. In the event of an overdose, the infusion should be discontinued, and other therapies administered concurrently that have vasodilatory effects should be discontinued. Volume repletion, either orally or intravenously, can be used to counter the clinical effects of HNO mediated vasodilation, but should be used with extreme caution in decompensated HF subjects. If marked hypotension occurs, appropriate treatment, including IV pressor agents may be required to support blood pressure.

Furosemide

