9.3 Treated (per protocol)

All randomized participants who were given both study treatments and completed the study as per protocol. Participants will be included in the treatment group they received in each period.

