Appendix 4: List of Tables, Figures, and Listings

List of Tables and Figures:		
Output	Title	Analysis Set
Section 14.1 – Disposition and Demographic Data		
Table 14.1.1	Summary of Analysis Sets	All Subjects
Table 14.1.2	Summary of Subject Disposition	All Subjects
Table 14.1.3.1	Summary of Demographics	Randomized
Table 14.1.3.2	Summary of Demographics	Per Protocol
Table 14.1.4	Summary of Dosing	Safety
Section 14.2 – Efficacy Data		
Table 14.2.1.1	Summary of Urinary Output	Per Protocol
Figure 14.2.1.2	Plot of Mean (+SD) Urinary Output over Time	Per Protocol
Figure 14.2.1.3.1	Barchart of Mean Urinary Output over Time	Per Protocol
Figure 14.2.1.3.2	Barchart of Individual Urinary Output over Time	Per Protocol
Table 14.2.1.4	Statistical Analysis of the Volumes of Urinary Excretion	Per Protocol
Figure 14.2.1.5	Plot of Paired Urinary Output by Treatment	Per Protocol
Figure 14.2.1.6	Q-Q-Plot of Difference BMS-986231 – Placebo	Per Protocol
Table 14.2.2.1	Summary of Fractional Excretion of FeNa and FeK	Per Protocol
Figure 14.2.2.2.1	Barchart of Mean Fractional Excretion over Time	Per Protocol
Figure 14.2.2.2.2	Barchart of Individual Fractional Excretion over Time	Per Protocol
Table 14.2.2.3	Statistical Analysis of the Fractional Excretion	Per Protocol
Figure 14.2.2.4	Plot of Paired Fractional Excretion	Per Protocol
Table 14.2.3.1	Summary of Natriuresis	Randomized
Figure 14.2.3.2	Plot of Paired Natriuresis	Randomized
Table 14.2.4.1	Summary of Furosemide Concentration and Ratio of Urinary Sodium to Urinary Furosemide	Randomized
Figure 14.2.4.2	Plot of Paired Furosemide Concentration and Ratio of Urinary Sodium to Urinary Furosemide	Randomized
Table 14.2.5	Summary of eGFR and Creatinine Levels	Randomized
Table 14.2.6	Summary of Renal and Urinary Biomarkers	Randomized
Table 14.2.7	Summary of Body Weight	Randomized
Table 14.2.8	Summary of Body Bio-Impedance	Randomized
Table 14.2.9	Summary of Ultrasound Indices of Congestion	Randomized
Table 14.2.10	Summary of Lung Ultrasound Indices of Pulmonary Congestion	Randomized
Table 14.2.11	Summary of Pulmonary B-lines	Randomized
Section 14.2 – Pharmacokinetic Data		
Table 14.2.12.1	Summary of Furosemide Plasma Concentrations	Randomized
Table 14.2.12.2	Summary of Furosemide Urine Recovery by Interval	Randomized

Table 14.2.12.3	Summary of Furosemide Urine Recovery	Randomized
Table 14.2.12.4	Summary of BMS-986231 and Metabolite Plasma Concentrations	Randomized

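### The 4-hour urine volume is tested only in a per-protocol set that leaves low-blood-pressure dose changes undefined, with no Randomized-set counterpart, and FeNa/FeK are moved to that set undeclared

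*Protocol*

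**What the plan says.** **Primary set.** Protocol 9.4.1.1: "All primary efficacy analyses will be performed using the treated (per protocol) population". SAP 15.1 repeats this and SAP 9.0 ticks only that set for the primary analysis. In SAP Appendix 4 the test itself, Table 14.2.1.4 ("Statistical Analysis of the Volumes of Urinary Excretion"), is assigned to Per Protocol, as are the other six urinary-output items.

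**Definition.** SAP 9.3, like protocol 9.2, takes "All randomized participants who were given both study treatments and completed the study as per protocol". Protocol 9.4 had said that the SAP "will describe the selection of participants to be included in the analyses", but SAP 9.3 adds nothing to the protocol's sentence. SAP 11.0 lists important deviations without linking them to set membership.

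**Dose changes.** Protocol 6.4 sets out reductions, interruptions and stops for low blood pressure, for example "Study drug is decreased by 50% if SBP decreases to levels <90 mmHg". It also says: "If an infusion in a given period is discontinued, patients remain eligible to complete the subsequent period". Protocol 8.3 notes that "BMS-986231 produces vasodilation as a component of its hemodynamic effects", and the first safety endpoint in protocol 9.3.3 is "Clinically relevant hypotension (defined as SBP < 90 mmHg or symptomatic hypotension) during infusion".

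**Secondary set.** Protocol 9.4.1.2 places secondary efficacy in the Randomized set. SAP 15.2 places FeNa and FeK in the per-protocol set. SAP 7.1 declares no departure from the protocol, although SAP 3.0 undertakes to identify substantial differences.

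**The concern.** The set has two conditions. Receipt of both treatments is easy to apply. Completion in line with the protocol is not, because the 6.4 changes are themselves protocol instructions. A patient whose infusion is stopped in one period may go on to the next, so the first condition can be met while the second stays open. The decision could then be taken after the volumes are known.

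The departures at issue can be effects of the drug. It dilates vessels, and the SBP level that triggers a dose reduction is the threshold used in the hypotension safety endpoint. If such patients are excluded, membership depends on a post-randomisation response to treatment, and in a crossover one event in the active period removes both of that patient's periods. With about 20 patients and no replacement (SAP 6.2), a few exclusions could change the estimated effect, which is a main product of a mechanistic phase 2 study.

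**Working it through.** **Inputs.** n = 20; SD of the change 20 to 35 mL/H; diuresis after the bolus 250 to 300 mL/H, so a 20% increase is 50 to 60 mL/H (protocol 9.1, SAP 6.1). Paired t-test (protocol 9.4.1.1), two-sided 0.05 (SAP 8.4.3). Neither document gives the number of patients excluded or their response, so those values are assumptions below.

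**1. The plan's own figure.** At the least favourable inputs the noncentrality is 50/35 × √20 = 6.39, and exact paired power is above 99.9%. The stated 90% is not reproduced; the plan's inputs imply more. Power stays high in a smaller set: 99.4% at n = 12, 97.9% at n = 10 and 93.1% at n = 8. Loss of power through exclusion is therefore not the issue.

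**2. Effect on the estimate.** Let k of 20 be excluded and f = k/20. If the excluded patients had no drug effect, the ratio of per-protocol to all-treated estimate is 1/(1 − f). If they had twice the effect of those kept, it is 1/(1 + f).

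| k | no effect in excluded | double effect in excluded |
|---|---|---|
| 1 | 1.05 | 0.95 |
| 2 | 1.11 | 0.91 |
| 4 | 1.25 | 0.83 |
| 6 | 1.43 | 0.77 |

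The direction depends wholly on the assumption.

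**3. When this would be noticeable.** The planned 95% CI half-width is t(0.975, 19) × SD/√20 = 2.093 × 20/4.472 = 9.4 mL/H, rising to 2.093 × 35/4.472 = 16.4 mL/H. To move the estimate by one half-width, the gap in effect between kept and excluded patients must be half-width × 20/k: 94 to 164 mL/H for k = 2, 47 to 82 for k = 4, and 31 to 55 for k = 6. Against a planned effect of 50 to 60 mL/H, one or two exclusions matter little; four or more could matter.

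**4. Does the test survive?** Take 14 patients at 50 mL/H and 6 at zero, SD 35. The mean is 0.7 × 50 = 35; the SD is √(35² + 0.3 × 0.7 × 50²) = 41.8; the half-width is 19.6; the 95% CI is about 15 to 55. The result holds. It becomes doubtful only if the excluded patients had a clearly reversed effect: with 4 of them at −50 mL/H the mean over all 20 is 30, the SD 53.2, and power 66.8%. Nothing in the documents supports such a value.

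**5. Sets side by side.**

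| Outputs in Appendix 4 | Number | Set in Appendix 4 | Elsewhere |
|---|---|---|---|
| Urinary output, 14.2.1.1 to 14.2.1.6 | 7 | Per Protocol | agrees |
| FeNa/FeK, 14.2.2.1 to 14.2.2.4 | 5 | Per Protocol | protocol 9.4.1.2: Randomized |
| Other efficacy, 14.2.3.1 to 14.2.11 | 11 | Randomized | SAP 9.0: per protocol |
| PK, 14.2.12.1 to 14.2.12.5 | 5 | Randomized | SAP 9.0: per protocol; SAP 16.0: Randomized |

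**The case against.** Five points deserve weight.

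- **The data are not hidden.** Protocol 9.4.1.1 has all data listed, and Appendix 4 plans listings of urinary output and its differences (16.2.6.1.1 and 16.2.6.1.2), analysis sets (16.2.3), drug administration (16.2.5.1) and hypotension (16.2.10.2), none marked as restricted to per protocol. SAP 10.0 and 14.0 tabulate set sizes and full-dose counts. With about 20 patients a reader could rebuild the all-patient difference. This stands, and rules out any claim that the excluded patients' results would be invisible. A listing still gives no prespecified estimate or interval.
- **The endpoint is on-treatment.** Protocol 9.3.1 defines output while on the drug, so a per-protocol primary analysis is coherent. A Randomized-set analysis answers a different question: the effect whatever dose was completed. This stands, and is why it should be added rather than substituted.
- **Exclusion is not shown.** A reader might infer that patients with dose changes will be dropped. The documents do not say so. Because 6.4 directs those changes, and the footnote to protocol Table 2 adapts assessment times after an early stop, keeping them is a natural reading. The fault is the ambiguity.
- **The FeNa/FeK choice is consistent within the SAP**, and SAP 3.0 says that the SAP supersedes the protocol's statistical considerations. What remains is an undeclared change.
- **The other set conflicts are mainly clerical.** They rest on two tick marks in SAP 9.0. For PK, SAP 16.0 and Appendix 4 agree. Much text after SAP 15.3 is redacted and may state a set. By title, all 16 outputs are summaries or plots, not tests.

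**Conclusion.** The concern holds in a limited form and should be settled before unblinding. The primary comparison is estimated and tested only in a set whose membership is undefined for events that the drug can cause, and no planned table, test or confidence interval gives it in the Randomized set. The FeNa/FeK set differs from the protocol without being declared. The SAP 9.0 ticks for other efficacy and PK are housekeeping.

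A reader might go further and conclude that the per-protocol result will favour the drug, or that its significance is unsafe. The documents support neither. They give no exclusion rate and no response in excluded patients, so direction and size cannot be derived. If the planning inputs are right and excluded patients have at worst no effect, significance would probably survive even 6 exclusions. The size of the estimate is what is exposed: 1.25 times the all-treated value with 4 of 20 excluded at zero effect, as an illustration and not a forecast.

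**What to change.** Edit the SAP before unblinding:

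1. **SAP 15.1 and Appendix 4.** Keep the per-protocol analysis as primary. Add a Randomized-set sensitivity table of the 4-hour volume. First use the same paired analysis in all patients with post-furosemide urine in both periods, whatever dose was completed, so that only the set changes. Then use a mixed model with patient as a random effect, which also uses patients with one period. State that this estimates the effect regardless of dose completed. Having a post-furosemide volume is itself a post-randomisation condition, so report by treatment how many patients have none.
2. **Shortened collections.** Protocol 4.1 collects urine until 2 hours after drug discontinuation, so with a bolus at H4 a stop at H6 or later still covers four hours, but an earlier stop may not. Do not count uncollected hours as zero. Compare mL/H over the hourly post-furosemide intervals collected in both periods of that patient, and state the assumption: that the treatment difference in the uncollected hours resembles that in the collected ones.
3. **SAP 9.3.** State whether changes made under protocol 6.4 count as per protocol.
4. **Sets.** Restore the Randomized set for FeNa/FeK, or show both sets and declare the change in SAP 7.1. Make SAP 9.0, 15.2, 16.0 and Appendix 4 agree.

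The cost is one or two extra tables on data already collected, a stated missing-data assumption, and a possibly less favourable estimate. N is unchanged. Given SAP 3.0, no protocol amendment is needed.
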